5.2.1 Exclusion Criteria Specific to Capecitabine

The subject must be excluded from receiving capecitabine if the subject:

- Requires concomitant use of phenytoin and/or warfarin due to reported increases in serum phenytoin levels and the international normalized ratio (INR) in patients receiving concomitant phenytoin and warfarin, respectively.
- Has a known hypersensitivity to capecitabine or to any of its components.
- Has a known hypersensitivity to 5-fluorouracil.

5.2.2 Exclusion Criteria Specific to Imatinib

The subject must be excluded from receiving capecitabine if the subject:

- Requires concomitant use of anticoagulation with warfarin. Patients who require anticoagulation should receive low molecular weight heparin.
- Has a left ventricular ejection fraction (LVEF) of < 45%
- Has New York Heart Association (NYHA) class III or IV symptoms
- Has had major surgery within 2 weeks prior to study entry
- Has a history of ventricular tachycardia, ventricular fibrillation, ventricular flutter, Torsades de Pointes, or long QT syndrome

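### Section 5.2.2 contradicts itself: its heading names imatinib, but its operative sentence excludes subjects from capecitabine

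*Combined protocol and SAP*

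**What the plan says.** The trial has a general exclusion list (Section 5.2) and three drug-specific lists (5.2.1 capecitabine, 5.2.2 imatinib, 5.2.3 ruxolitinib).

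The second drug-specific list is headed "5.2.2 Exclusion Criteria Specific to Imatinib". The sentence that introduces its bullets is "The subject must be excluded from receiving capecitabine if the subject". Five criteria hang on that sentence:

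- the anticoagulant criterion: "Requires concomitant use of anticoagulation with warfarin"
- the ejection-fraction criterion: "Has a left ventricular ejection fraction (LVEF) of < 45" (per cent)
- the heart-failure criterion, which is NYHA class III or IV
- the surgical criterion, which covers major operations in the 2 weeks before entry
- the rhythm criterion: "Has a history of ventricular tachycardia, ventricular fibrillation, ventricular flutter, Torsades de Pointes, or long QT syndrome"

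Section 5.2.1 opens with the identical sentence. There it agrees with its heading and with its own bullets, for example "Has a known hypersensitivity to capecitabine or to any of its components". Section 5.2.1 also excludes subjects who need warfarin. Section 5.2.3 has two bullets and no introductory sentence.

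On cardiac screening, footnote p to the general calendar (Table 6, Section 9.1) requires a baseline transthoracic echocardiogram for imatinib-treated subjects.

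**The concern.** The heading and the operative sentence name different drugs, and both cannot govern the list. The text is operative, not background. Under Section 6.1 a physician investigator signs a protocol-specific eligibility checklist, source documents are supplied for each item, and a registrar verifies eligibility before therapy may begin. Under Section 11.3, deviations and eligibility waivers go to the data and safety monitoring committee. Whether giving a particular drug to a subject with a low ejection fraction counts as a deviation depends on which half of 5.2.2 is followed.

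Safety is at stake first, because four of the five criteria concern cardiac status or recent surgery. The counts come second. Who may start a matched drug feeds the feasibility endpoint, and who is treated feeds the response-rate denominator.

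**Working it through.** There is no stated figure to reproduce. The check sets the passages side by side.

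**1. Lead-ins of the three drug-specific lists**

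| Section | Drug in heading | Drug in lead-in | Agree? |
|---|---|---|---|
| 5.2.1 | capecitabine | capecitabine | yes |
| 5.2.2 | imatinib | capecitabine | no |
| 5.2.3 | ruxolitinib | no lead-in | cannot be judged |

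The sentence in 5.2.2 is complete and matches 5.2.1 word for word. A gap in text extraction or a redaction would not produce that; a lead-in carried over from 5.2.1 would.

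**2. What each bullet does if the lead-in is taken literally**

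| Criterion in 5.2.2 | Effect on capecitabine | Drug-specific sentence applying it to imatinib |
|---|---|---|
| Warfarin | largely repeats 5.2.1 | none |
| Ejection fraction below 45% | new restriction | none |
| NYHA class III or IV | new restriction | none |
| Major surgery within 2 weeks | new restriction | none |
| Ventricular arrhythmia or long QT | new restriction | none |

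So 5 − 1 = 4 bullets add a restriction on capecitabine, and 0 of 5 are tied to imatinib by an operative sentence.

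**3. Is imatinib covered elsewhere?** The imatinib text in 4.3.2, 4.5.2, 4.6.2, 4.7.2, 4.8.2 and 4.9.3 deals with dosing, pharmacology, handling, sampling and dose modification. None of it states an imatinib-specific exclusion. The general list in 5.2 has no ejection-fraction, NYHA, arrhythmia, warfarin or recent-surgery criterion. It does have an item letting the investigator exclude a subject for any condition or therapy that makes participation unsuitable. The coagulation rows of Table 5 (Section 5.1) allow for subjects on anticoagulants, so they do not replace the warfarin bullet.

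**4. Do the calendars settle it?**

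| Table | Cardiac screening row |
|---|---|
| 6, general | ECG and echocardiogram, with footnote p limiting the echocardiogram requirement to imatinib |
| 7, capecitabine | 12-lead ECG only |
| 8, imatinib | 12-lead ECG only |
| 9, ruxolitinib | 12-lead ECG and echocardiogram |

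Footnote p links cardiac imaging to imatinib, but the imatinib calendar omits the echocardiogram and the ruxolitinib calendar includes it. The literal reading of 5.2.2 also lacks support: the capecitabine calendar schedules no echocardiogram from which an ejection fraction could be read. The three agent calendars refer the reader to Table 4 as the general calendar. Table 4 is the ruxolitinib thrombocytopenia table, so the pointer does not lead to footnote p.

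**5. Scale in the counts, for orientation only.** With 30 enrolled, one subject is 1/30 = 3.3 percentage points of the feasibility rate. With the planning minimum of 9 treated, and all 9 evaluable, one subject is 1/9 = 11.1 points of the response rate. The documents do not say how often the listed conditions occur or how often imatinib is matched. The expected number of affected subjects therefore cannot be derived, and it may be zero.

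**The case against.** The strongest reply is that this is a clerical slip whose intent is plain. The heading is protocol text too. In 5.2.3 the heading alone tells the reader which drug the list governs, and the same could be said of 5.2.2. Footnote p supports that reading. Drug selection also passes through a tumor board whose first listed criterion is patient safety, and a registrar can raise queries before enrollment. All of this stands, and it makes a literal misreading less likely. It does not remove the contradiction, because the calendars disagree with footnote p on which subjects have an echocardiogram.

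A reader might go on to infer four stronger things, and the documents support none of them:

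- **That nothing keeps a subject with these conditions off imatinib.** The general exclusions, including the investigator-opinion item, apply whatever the drug. What is missing is an unambiguous drug-specific sentence.
- **That all five criteria impose a mistaken restriction on capecitabine.** Warfarin users are already excluded from capecitabine by 5.2.1, so at most four bullets add anything there.
- **That the eligibility checklist carries the error.** The checklist is not among the documents. It can be checked but not presumed wrong.
- **That the co-primary analyses are compromised.** No sample size, power, alpha or endpoint definition depends on this sentence, and no number in the documents shows an effect on the counts.

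**Conclusion.** Wrong as written: Section 5.2.2 is internally inconsistent in operative, safety-relevant eligibility text. Five criteria are affected. On the literal reading four newly restrict capecitabine, one is largely redundant, and none is applied to imatinib by a drug-specific sentence. The heading and footnote p point to imatinib as the intended drug, but the agent calendars do not bear this out consistently. Which drug each criterion should govern is a clinical matter for the sponsor and is not decided here.

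The conclusion rests on the wording of Sections 5.2 to 5.2.3 and on the calendar row labels and footnote p as they appear in the document. It assumes that no separate document, such as the checklist or a drug sub-protocol, already resolves the conflict. The correction should be made, but it is not a reason to question the statistical design.

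**What to change.** 1. Reconcile the heading and lead-in of 5.2.2 so that both name the same drug.
2. Reconcile that text with footnote p and with the ECG/echocardiogram rows of Tables 6 to 9, so that any criterion needing an ejection fraction has a scheduled measurement in the matching calendar. Correct the calendars' reference to Table 4 at the same time.
3. Check whether 5.2.3 needs an introductory sentence.
4. Check the eligibility checklist against the reconciled text and amend it only if it differs. If any subjects have already been registered to capecitabine or imatinib, check their eligibility against the same text.

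The cost is a few lines of protocol text, possibly a calendar row, and submission of the amendment to the IRB as Section 13 requires. The sample size and analysis are unchanged.

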5.2.3 Exclusion Criteria Specific to Ruxolitinib

- Has a history of hypersensitivity to ruxolitinib or to any medicine with similar chemical compounds
- Has a baseline corrected QT interval (QTc) > 470 ms

5.3 Inclusion of Women and Minorities

Both men and women of all races and ethnic groups are eligible for this trial.

Accrual Targets										
Ethnic Category	Sex/Gender									
Lunic Category	Females		Males		Total					
Hispanic or Latino	7	+	8		15					
Not Hispanic or Latino	8	+	7	_	15					
Ethnic Category: Total of all subjects	15	+	15		30					
Racial Category										
American Indian or Alaskan Native	3	+	3		6					
Asian	3	+	3		6					
Black or African American	3	+	3		6					
Native Hawaiian or other Pacific Islander	3	+	3		6					
White	3	+	3	_	6					
Racial Category: Total of all subjects	15	+	15	_	30					

5.4 Subject Recruitment

This study will be conducted at Columbia University Medical Center. Thirty subjects will be needed to meet the primary study endpoint. The amount of time required to complete this trial will depend on the rapidity of accrual. We estimate evaluation of 3-5 subjects of a month in our Pancreas Center with enrollment of 1-2 subjects a month to complete accrual over 30 months.

Subjects will be followed for 30 additional days after completion or early discontinuation of treatment for safety follow-up, after which they will be off the active treatment phase of the study. Post-treatment long-term follow-up for disease status and survival will proceed until the subject has withdrawn consent, is lost to follow-up, has died, or until the Sponsor makes a decision to close the study.

Participation is voluntary. The patient must be aware of the neoplastic nature of his/her disease and willingly consent after being informed of the procedures to be followed, the experimental

nature of the therapy, alternatives, potential benefits, side effects, risks, and discomforts. The investigatory will make certain that an appropriate informed consent process is in place to ensure that potential research subjects, or their authorized representatives, are fully informed about the nature and objects of the clinical study, the potential risks and benefits of the study participation and their rights as research subjects.

5.5 Treatment Discontinuation

Subjects may withdraw from treatment at any time for any reason. A subject may be dropped from the trial at the discretion of the investigator should any untoward effect occur. Additionally, a subject may be withdrawn by the investigator or Sponsor if enrollment into the trial is inappropriate, the trial plan is violated, or for administrative and/or other safety reasons.

The investigator must discontinue study treatment for any of the following reasons:

- Subject or or legal representative desires discontinuation of treatment (i.e., withdraws consent for treatment)
- Radiographic disease progression (if confirmed by RECIST v1.1)
- Unacceptable toxicity
- Noncompliance with study procedures, including administration of nonprotocol therapies
- Requirement for alternative therapy
- Intercurrent illness or worsening of a chronic condition that prevents further administration of treatment
- The subject has a confirmed positive serum pregnancy test
- Subject is lost to follow-up

The reason for withdrawal from treatment will be documented in the CRF. Posttreatment followup for disease status and survival will continue until death unless any of the criteria for early study withdrawal are met (Section 10.9)

Discontinuation of treatment due to progression should be recorded on the Treatment Disconinuation CRF as "Disease Progression" and not as an AE or a SAE (unless the event meets the criteria for SAE as outlined in Section 8.1).

If the reason for withdrawal is AE, the subject will be followed by the Investigator as described in Section 8 until such events resolve, stabilize, and, according to the Investigator's judgment, there is no need for further follow-up.

5.6 Early Study Withdrawal

When a subject discontinues/withdraws prior to trial completion, all applicable activities scheduled for the final trial visit should be performed at the time of discontinuation. Any AEs which are present at the time of discontinuation/withdrawal should be followed in accordance with the safety requirements outlined in Section 8 Assessing and Recording Adverse Events.

Subjects who discontinue for toxicity but do not withdraw consent from the study will continue to be followed for post-study treatment and survival as described in the Trial Flow Chart (Section 9).

5.7 Data Collection and Follow-Up of Withdrawan Subjects

The End of Treatment and Follow-Up visit procedures are listed in Section 9 (Trial Flow Chart) and Section 9.2 (Administrative Procedures). After the end of treatment, each subject will be followed for 30 days for adverse event monitoring (SAEs will be collected for 30 days after the end of treatment as described in Section 8). Subjects who discontinue for reasons other than progressive disease will have post-treatment follow-up for disease status until disease progression, initiating a non-study cancer treatment, withdrawing consent, or becoming lost to follow-up. After documented disease progression, each subject will be followed by telephone for survival until death, withdrawal of consent, or the end of the study, whichever occurs first.

5.8 **Post-Treatment Visits**

5.8.1 Safety Follow-Up Visits

The mandatory Safety Follow-Up Visit should be conducted approximately 30 days after the last dose of trial treatment or before the initiation of a new anti-cancer treatment, whichever comes first.

All AEs that occur prior to the Safety Follow-Up Visit should be recorded. Subjects with an AE of Grade ≥ 2 will be followed until the resolution of the AE to Grade 0-1 or until the beginning of a new anti-cancer therapy, whichever occurs first. SAEs that occur within 90 days of the end of treatment or before initiation of a new anti-cancer treatment should also be followed and recorded.

5.8.2 Follow-Up Visits

Subjects who discontinue trial treatment for reasons other than disease progression will move into the follow-up phase and should be assessed Q8W by radiologic imaging to monitor disease status. Every effort should be made to collect information regarding disease status until the start of a new anti-cancer therapy, disease progression, death, or the end of the study.

Information regarding post study anti-cancer treatment will be collected if new treatment is initiated.

5.8.3 Survival Follow-Up

Subjects who experience disease progression (by site assessment) or start a new anti-cancer therapy, will move into the survival follow-up phase. Subjects should be contacted (e.g., by telephone or visit) approximately every 12 weeks to assess for survival status until death, withdrawal of consent, or the end of the study, whichever occurs first. This will be done via telephone calls, subject medical records, and/or clinical visits. If the subject specifically withdraws consent from survival follow-up, the study staff may use a public information source (e.g. county records) to obtain information about survival status only.

Post study anti-cancer therapy will be collected during survival follow-up.

6. REGISTRATION PROCEDURES

6.1 CUMC Research Participant Registration

Confirm eligibility as defined in the section entitled Criteria for Subject Eligibility.

Obtain informed consent, by following procedures defined in section entitled Informed Consent Procedures, along with applicable institutional policies and federal regulations.

Only Investigators/Research personnel properly trained and delegated to consent subjects for this protocol will participate in the consenting process. Furthermore, properly delegated/trained Physician Investigators (e.g., MD, MD PhD) are required to sign/verify a protocol specific Eligibility Checklist for each subject enrolled on the study, in addition to providing the relevant source documentation confirmation subject eligibility.

All participants must be centrally registered through the Central Registration Office within Herbert Irving Comprehensive Cancer Center at CUMC prior to initiation of study treatment.

Registration hours are available Monday through Friday from 9:00am – 5:00pm EST (excluding holidays and weekends). Same day patient registrations (and after hour registrations) will be accommodated on a case by case basis provided that the study team has expressed all time sensitive registration concerns/cases in a timely manner to the Central Registration Office.

CPDM Central Registration Procedures:

Within 48 hours of obtaining consent (excluding holidays and weekends), a completed/signed IRB approved informed consent HIPAA form, and demographics forms must be submitted to the CPDM Central Registration Office via an email to [contact] or fax to [contact], with the subject line "AAAxxxx Pending Subject Registration Request (PHI)". Upon receipt, applicable subject information as well as a "pending eligibility" status will be entered into HICCC's institutional database. This status will remain until further source documentation is made available to confirm overall patient eligibility. Required materials for all pending registration submissions are as follows:

• Completed/signed IRB approved/stamped Informed Consent Forms, including additional study ICFs (e.g., tissue, DNA, etc.), as applicable.

- The completed/signed IRB approved HIPAA Authorization form
- Completed/signed CPDM ICF checklist
- Completed/signed HICCC personal census form
- Completed/signed CPDM Demographics Note to File

In order to confirm eligibility status, Investigators/designees (e.g., study specific Clinical Research Coordinator/Research Nurse, etc.) must submit the following documentation to the Central Registration Office via email or fax:

• The completed/signed study specific Eligibility Checklist (signed by an Physician level Investigator)

• Copies of source documentation necessary for each item to be verified on the CPDM specific Eligibility Checklist, including but not limited to:

• Copy of required laboratory test and procedure reports (e.g., hematology, serum chemistry, pregnancy test when applicable, MRI reports, CT/bone scans, etc.)

• Copy of pathology and surgical reports

• Copy of clinic note(s) or other appropriate medical records capturing the consent process information, along with providing source documentation of any other items needed for screening/eligibility that are not captured in other source document forms (e.g., positive investigator statements of unique eligibility items not captured via other direct source documentation, concomitant medication lists, etc.)

• Protocol deviation/waiver approvals (if applicable)

• Please note: subject line of email or fax should include the following: "AAAxxxxx Complete Subject Registration Request (PHI)".

Upon receipt of the above mentioned documentation, participant eligibility information will be verified by a qualified Central Registration Registrar. If any questions arise during the review process, queries in the form of emails will be addressed to the applicable study team personnel for clarification prior to enrollment. All applicable finalized registration/eligibility information will then be entered into HICCC's institutional CTMS database by the Central Registration Registrar. Upon completion, an official subject registration notification email will be sent to the PI/research team which will include eligibility/enrollment status, as well as subject ID information. Protocol therapy may not be initiated prior to receipt of this notification from the Central Registration Office.

All screen fail/ineligible subjects, as well as subject's who withdraw consent prior to enrollment/initiation of protocol therapy must be submitted to the Central Registration office in a manner analogous to the procedures noted above. Applicable source documentation will be required within the corresponding submissions.

7. TREATMENT PLAN

7.1 Study Treatment

The results of the OncoTreat analysis will include on FDA-approved or investigational oncology drugs. These results, along with the preclinical validation studies using PDX/PDO models, will be discussed at the PMTB. Details of the trial design are discussed in Section 4.1.

7.2 **Duration of Therapy**

In the absence of treatment delays due to adverse events, treatment may continue until one of the following criteria applies:

- Disease progression
- Intercurrent illness that prevents further administration of treatment
- Unacceptable adverse events(s)
- Patient decides to withdraw from the study
- General or specific changes in the patient's condition render the patient unacceptable for further treatment in the judgment of the investigator

7.3 Duration of Follow Up

Patients will be followed for 4 weeks after completion or removal from study or until death, whichever occurs first. Patients removed from study for unacceptable adverse events will be followed until resolution or stabilization of the adverse event.

7.4 Criteria for Removal from Study

Patients will be removed from study when any of the criteria listed in Section 5.4 applies. The reason for study removal and the date the patient was removed will be documented in the Case Report Form.

8. ADVERSE EVENTS: LIST AND REPORTING REQUIREMENTS

8.1 Definitions

8.1.1 Adverse Event

An adverse event (AE) is any untoward or unfavorable medical occurrence in a human subject, including abnormal sign, symptom or disease, temporally associated with the subject's participation in research, whether or not considered related to the subject's participation in the research. Abnormal results of diagnostic procedures are considered to be adverse events if the abnormality:

- Results in study withdrawal
- Is associated with a serious adverse event
- Is associated with clinical signs or symptoms
- Leads to additional treatment or to further diagnostic tests
- Is considered by the investigator to be of clinical significance

8.1.2 Serious Adverse Event

Adverse events are classified as serious or non-serious. A serious adverse event (SAE) is any AE that is:

- Fatal
- Life-threatening
- Requires inpatient hospitalization/prolongation of existing hospitalization, unless:
 - Routine treatment or monitoring of the studied indication, not associated with any deterioration in condiction (procedures such as central line placements, paracentesis, pain control)
 - Elective or pre-planned treatment for a pre-existing condition that is unrelated to the indication under study and has not worsened since the start of study drug
 - Treatment on an emergency outpatient basis for an event not fulfilling any of the definitions of an SAE given above/below and not resulting in hospital administrations
 - Social reasons and respite care in the absence of any deterioration in the patient's general condition
- Results in persistent or significant disability or incapacity
- A congenital anomaly or birth defect
- An important medical event

Important medical events are those that may not be immediately life threatening, but are clearly of major clinical significance. They may jeopardize the subject, and may require intervention to prevent one of the other serious outcomes noted above. For example, drug overdose or abuse, a seizure that did not result in in-patient hospitalization or intensive treatment of bronchospasm in an emergency department would typically be considered serious.

All adverse events that do not meet any of the criteria for serious events should be regarded as non-serious adverse events.

